6.5.4 Laboratory Parameters

Clinical laboratory (hematology, serum chemistry, and urinalysis) results will be obtained at screening and at early termination or end of study (post-VFSS 2).

Serum chemistry parameters include the following: alanine aminotransferase (ALT), albumin, aspartate aminotransferase (AST), urea, chloride, creatinine, creatinine kinase, potassium, sodium, bicarbonate, magnesium, bilirubin, and serum pregnancy test.

Hematology parameters include the following: hematocrit, hemoglobin, platelet count, red blood cell count, red blood cell indices (mean corpuscular volume [MCV], mean corpuscular hemoglobin [MCH], mean corpuscular hemoglobin concentration [MCHC]), neutrophils, lymphocytes, monocytes, eosinophils, basophils, and white blood cell count with differential.

Urinalysis parameters include the following: color and clarity, pH, specific gravity, protein, glucose, ketones, bilirubin, occult blood, nitrite, urobilinogen, leukocytes, and urine pregnancy test. Unless otherwise specified, microscopic examination will be performed on abnormal finding.

Listings of all clinical laboratory results will be provided with the abnormal values flagged with "L" for low and "H" for high for continuous parameters, and "A" for abnormal for categorical parameters.

6.5.5 ALS Functional Rating Scale – Revised (ALSFRS-R)

The ALSFRS-R is a quickly administered (5 minute) ordinal rating scale (ratings 0-4) used to determine subjects' assessment of their capability and independence in 12 functional activities/questions performed at screening, and at Visit 1 pre-VFSS 1. All 12 activities are relevant in ALS.

Descriptive statistics (sample size, median, Min and Max,) will be presented for screening, and at Visit 1 pre-VFSS 1 as appropriate.

A listing of ALSFRS-R results will also be provided, as an overall score, as individual question scores, and by individual functional domains.

6.5.6 Functional Oral Intake Scale – FOIS

The FOIS is a simple 7 point scale that describes the subject's functional status with respect to oral intake, ranging from 1 (No oral intake) to 7 (Total oral intake with no restrictions), and will be administered at Screening, and at Visit 1 pre-VFSS 1.

Number and percentage of subjects will be presented for each point on the scale for screening, and for Visit 1 pre-VFSS 1 as appropriate.

A listing of FOIS results will also be provided.

6.5.7 Eating Assessment Tool 10 – (EAT-10)

The Eating Assessment Tool-10, is a validated 10-item patient report scale of perceived swallowing impairment, and will be administered at Screening, and at Visit 1 pre-VFSS 1. The EAT-10 uses a 5-point ordinal rating scale where a patient rates their perceived degree of impairment for each item from 0 (no impairment) to 4 (severe impairment) for a total range of scores between 0 (no perceived swallowing impairment) to 40 (severe impairment).

Descriptive statistics (sample size, median, Min and Max,) will be presented for screening, and for Visit 1 pre-VFSS 1 as appropriate.

A listing of EAT-10 results will also be provided.

6.5.8 Statistical Analyses

The primary objective is to assess the effect of the ROSF formulation, if any, of a single 50 mg dose of ROSF on swallowing safety in subjects with ALS. The analyses will be descriptive only, and not hypothesis-testing.

The PAS scores obtained in swallow tests during VFSS 1-PAS (before ROSF) and VFSS 2-PAS (after ROSF) will be compared within each subject and across subjects.

Swallowing Evaluation Results:

There is considerable discussion in the literature regarding the psychometric properties and optimal/correct ways to analyze PAS scores (an 8-point ordinal scale, where higher scores indicate lower function, measured individually for 11 swallowing trials). There is no method universally accepted as best due to the psychometric and clinical characteristics of the PAS. The three methods described below will be used to present the results of this study. This approach was determined *post hoc*, at the time of examining results for the first seven patients.

“Single worst score” method:

A number of publications use the single worst score on any swallowing trial as an indicator of PAS swallowing function. Results presented will include the number/percentage of patients who stay the same, increase or decrease (and by how many points).

“Sum of scores” method:

The sum of 11 PAS scores will be used. Results presented will include the number/percentage of patients who stay the same, increase or decrease sum (and by how much).

“Steele 4-category” method:

Steele and associates (Dysphagia 2017) propose categorization of single worst PAS score into 4 categories. Steele A includes scores 1, 2, 4; Steele B includes 3, 5, 6; Steele C includes a score

of 7 and Steele D includes a worst score of 8. Results presented will include the number/percentage of patients who stay the same, increase or decrease (and by how much).

Interim Analyses:

An unofficial interim analysis was performed after 7 patients had completed the study. As previously mentioned, these results were discussed with the FDA and they agreed with the Sponsor that the study should be terminated after the two additional patients who had been screened but not yet completed were evaluated with the VFSS.

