The primary objective is to assess the effect of the ROSF formulation, if any, on swallowing safety in subjects with ALS. The null hypothesis is that there will be no difference between the PAS scores (i.e. swallowing safety) obtained before and after administration of the study medication.

The PAS scores obtained in swallow tests during VFSS 1-PAS (before ROSF) and VFSS 2-PAS (after ROSF) will be compared within each subject with the non-parametric Wilcoxon Signed-Rank Test. Alpha will be set at 0.05, two-tailed. Analysis across each swallowing trial will be performed, providing 12 bolus stimuli trials and approximately 35 swallows and PAS scores for each elicited swallow across testing within each participant (across various textures and swallowing complexities given that multiple swallows are typically elicited per bolus stimuli trial) to ensure a comprehensive exam across a variety of liquid volumes, textures and consistencies).

CONFIDENTIAL INFORMATION

The information in this study protocol is confidential. Any disclosure, copying or distribution of the information contained within is strictly prohibited without written consent from MonoSol Rx LLC.

Sample size was determined for a within-person design (repeated measures, same subjects in VFSS 1-PAS and VFSS 2-PAS) using G*Power Version 3.1.9.2, assuming a correlation = 0.6 across the two measurements. A sample size of n=25 would be able to detect at least a 1.0 point difference (two-tailed), effect size 0.6, in PAS scores from Test 1 and Test 2 with 80% power. It is anticipated that approximately 20% of recruited ALS subjects will grossly aspirate during VFSS 1-PAS and will not have a VFSS 2-PAS performed (for both safety reasons and also because Test 2 would not yield any useful data due to a ceiling effect). Therefore enrollment is planned for a total of 30 subjects to account for this potential.

Depending on the study enrollment rate, the Sponsor may elect to perform an interim analysis using available data from the subset of subjects who have completed the study at that time. The results of this interim analysis will be used only for internal planning and possibly for sharing with regulatory authorities. The results of the interim analysis will have absolutely no influence on the subsequent conduct of the study.

The following safety information will be included as descriptive summaries:

- Type, incidence, and severity of adverse events
- Physical and neurological examinations

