13.5. Data Analyses

13.5.1. Penetration Aspiration Scale (PAS)

Following the examination, each recorded swallow trial will be spliced by bolus trial and further by individual swallow and coded for subsequent evaluation. This will include splicing and coding of each bolus trial per patient (n=12 per VFSS test). Further, each individual swallow within a bolus trial will be analyzed (this can range between 1 to 7 swallows per bolus trial). Frame-by-frame analysis at 30 frames per seconds will be utilized. Two independent, blinded, and experienced raters from the PI's laboratory will perform analyses. Discrepancies between raters will be flagged and resolved at a consensus meeting and three swallows from each evaluation will be repeat rated at random for evaluation of intra-rater reliability.

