13.5.2. Statistical Analysis

The within subject difference in PAS scores (before and after ROSF) is the primary outcome to assess swallowing safety of ROSF in subjects with amyotrophic lateral sclerosis. Data will be analyzed using the non-parametric Wilcoxon Signed-Rank Test. Alpha will be set at 0.05. Analysis across each swallowing trial will be performed, providing 12 bolus stimuli trials and approximately 35 swallows and PAS scores for each swallow within each participant (across various textures and swallowing complexities) to ensure a comprehensive exam across a variety of liquid volumes, textures and consistencies). A sample size of 25 subjects is estimated to provide 80% power to detect an intra-subject difference of one point on the PAS at the 0.05 level (two-tailed). Additional details will be provided in the statistical analysis plan.

Depending on the study enrollment rate, the Sponsor may elect to perform an interim analysis using available data from the subset of subjects who have completed the study at that time. The results of this interim analysis will be used only for internal planning and

CONFIDENTIAL INFORMATION

The information in this study protocol is confidential. Any disclosure, copying or distribution of the information contained within is strictly prohibited without written consent from MonoSol Rx LLC.

possibly for sharing with regulatory authorities. The results of the interim analysis will have absolutely no influence on the subsequent conduct of the study.

Summary Statistics will be provided for the following:

- Demographic information
- Type, incidence, and severity of adverse events
- Physical and neurological examinations including oral examination
- Vital signs (heart rate, blood pressure, respiration rate, temperature),
- Clinical laboratory evaluation(s) and urine pregnancy test (females of childbearing potential)
- ALS Functional Rating Scale – Revised (ALSFRS-R)
- Eating Assessment Tool -10 (EAT-10)
- Functional Oral Intake Scale (FOIS)

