3. STUDY DESIGN

3.1 General Design

This is a single site, phase 2, single dose, open-label safety study to evaluate the effect of Riluzole Oral Soluble Film (ROSF) on swallowing safety in individuals with Amyotrophic Lateral Sclerosis (ALS). The original plan called for approximately 30 subjects with ALS to be enrolled, with a goal of 25 completed subjects after allowance for dropouts. These subjects were to undergo a clinical evaluation including the validated Amyotrophic Lateral Sclerosis Functional Rating Scale-Revised (ALSFRS-R). Swallowing safety will be assessed using the gold standard Videofluoroscopic Swallowing Study (VFSS) to afford direct visualization of the swallowing process and any episodes of penetration or aspiration will be quantified using the validated Penetration Aspiration Scale (PAS). Subjects will undergo a standardized protocol that includes 11 bolus stimuli presentations of different liquid and food materials to test the swallow across a continuum of textures and materials. Immediately following this, subjects will be given a single dose of ROSF 50 mg, placed on the median lingual sulcus of the dorsum of the tongue. Three minutes after the administration of ROSF, the identical standardized VFSS protocol will be re-administered to allow a comparison of swallowing safety (using the PAS scale) pre vs. post ROSF administration.

The study visit duration is expected to be approximately 30 days from time of screening to completion of study.

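### The SAP reports PAS only as a worst score, four categories of that worst score, and a sum of 11, so no stated output uses the bolus-by-bolus matching of the two exams

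*SAP*

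**What the plan says.** Protocol 13.5.2 makes the within-subject PAS difference the primary outcome and states: "Analysis across each swallowing trial will be performed, providing 12 bolus stimuli trials and approximately 35 swallows and PAS scores". Its reason is to obtain a "comprehensive exam across a variety of liquid volumes, textures and consistencies". The test is a single one: "Data will be analyzed using the non-parametric Wilcoxon Signed-Rank Test", with the synopsis adding "Alpha will be set at 0.05, two-tailed". Protocol 10.2.2.1 fixes the bolus order and requires the identical sequence at VFSS 2. Protocol 13.5.1 has recordings spliced and scored by bolus and by swallow, where "this can range between 1 to 7 swallows per bolus trial".

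SAP 3.1 says the boluses are there "to test the swallow across a continuum of textures and materials". SAP 6.6 cuts the list from 12 to 11. SAP 6.5.8 says PAS is scored separately on each of the 11 trials and will be compared within and across subjects, descriptively only. It then names three presentations, openly described as chosen after the first seven patients' results were seen:

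- the "single worst score on any swallowing trial as an indicator of PAS swallowing function";
- the sum of the 11 scores;
- four categories of the single worst score (A = 1, 2, 4; B = 3, 5, 6; C = 7; D = 8).

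Each is reported as the number of patients unchanged, increased or decreased, and by how much. The SAP promises listings for vital signs, laboratory results, ALSFRS-R (down to single questions), FOIS and EAT-10. It states none for PAS. Table and listing shells are in a separate document (SAP 6.5).

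**The concern.** Because both exams present the same boluses in the same order, bolus k before the film is the natural control for bolus k after it. The three SAP presentations do not use that matching. Two of them depend on one number, the maximum, and the third is a total in which gains and losses offset each other.

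The study stopped at 9 subjects, citing no signal of harm (SAP 1), and hypothesis testing was dropped. The safety conclusion on swallowing therefore rests on description alone. A description that can hide worsening on pudding behind an already abnormal thin-liquid swallow, or net it against an improvement elsewhere, is weaker than the data allow. SAP 6.6 does not say that the per-trial level has gone.

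**Working it through.** **Plan's own figure (background, not disputed).** Effect size 0.6, two-sided alpha 0.05, power 80%, n = 25 (Protocol 13.5.3). With the noncentral t and a Wilcoxon efficiency of 3/π, n = 25 gives 80.1% power, so the figure reproduces. It is sized for one pre/post difference per subject.

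**What each method can see.** Let x be the 11 pre-dose scores and y the 11 post-dose scores.

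- Worst score: max(y) − max(x). Any y at or below max(x) leaves it unraised.
- Four categories: a function of max(x) and max(y) only, so it has the same blind spot.
- Sum: Σy − Σx. If one bolus rises and none falls, this is at least +1. A check on 200,000 random vectors found no exception.

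**Constructed cases** (boluses 1-5 thin liquid, 6-8 thin honey, 9-10 pudding, 11 cracker):

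| Case | Worst | Category | Sum |
|---|---|---|---|
| Bolus 1 stays at 3; cracker 1→3; rest 1 | 3→3 | B→B | 13→15 |
| Bolus 1 3→1; cracker 1→3; rest 1 | 3→3 | B→B | 13→13 |
| Bolus 4 3→1; bolus 5 stays at 5; pudding (bolus 9) 1→3; rest 1 | 5→5 | B→B | 17→17 |
| Last case, but bolus 4 stays at 3 | 5→5 | B→B | 17→19 |

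In every row a semi-solid bolus moves from safe (1) to unsafe (3) by Table 4 of the protocol. All three methods read unchanged only in rows 2 and 3, where a thin-liquid improvement offsets it exactly. In rows 1 and 4 the sum rises but does not name the texture. Netting can also reverse the sign: pre 3,3,2,2 then seven 1s (sum 17), post 3,1,1,1,1,1,1,1,3,2,1 (sum 16), maximum 3 both times. One pudding bolus worsened to 3 and the sum fell.

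**How often (illustration; no PAS distribution is in the documents).** Assumptions: boluses independent; safe = 1; unsafe scores equally likely from 3 to 7; chance of 3 or more on each of boluses 6-11 rising from 2% to 10%; thin-liquid chance 5% to 30% at both exams. Among subjects newly at 3 or more on boluses 6-11:

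- worst score does not rise: 12% to 44%;
- neither worst score nor sum rises: 9% to 22%;
- all three methods unchanged: about 2% to 3%.

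Other mixes of scores widen these to 12%-83%, 9%-31% and 2%-19%. The upper 83% can be checked by hand: if every unsafe score is 3, the worst score fails to rise whenever a thin-liquid bolus was already unsafe, which at 30% per bolus is 1 − 0.7⁵ = 0.83.

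A second illustration assumed no drug effect and three score distributions (50% to 90% of scores equal to 1). Given that at least one texture's worst score rose, the worst score overall did not rise in 34% to 52%, the sum did not rise in 31% to 46%, neither rose in 28% to 36%, and all three were unchanged in 1% to 7%.

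**Matched data available.** 9 subjects × 11 boluses = 99 pairs at most. Either exam can end early under the bail-out rule in Protocol 10.2.2.1, so the count may be lower.

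**The case against.** A reader might infer that worsening confined to one texture is invisible under the SAP. It is not: with nothing improving, the sum must rise, and the SAP reports by how much. Unchanged on all three methods needs an unmoved maximum and an exact offset, which is uncommon in most settings tried.

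A reader might also infer that the protocol specified a comparison for each bolus and the SAP removed it. The protocol says analysis across each swallowing trial, with one Wilcoxon test and power for one pre/post difference. It states no per-bolus or per-texture contrast, and the objective is swallowing safety overall.

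Other points are fair. SAP 1 says the plan changed, and SAP 6.5.8 discloses that its methods are post hoc and descriptive. The separate shells may contain a PAS listing. The rates above assume the two exams are independent. In a variant with unsafe scores equally likely from 3 to 8, counting any bolus 6-11 newly at 3 or more, the neither-rises rate falls from 12%-24% to 9%-18% at a latent per-bolus correlation of 0.6, and to 4%-10% at 0.9. With 9 subjects a by-bolus table has small cells and supports no inference.

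All of this limits the strength of the point. None of it supplies a stated matched comparison, and a listing that may exist in the shells is not a commitment in the plan.

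**Conclusion.** The point holds in a limited form. No output stated in SAP 6.5.8 keeps the per-trial level the protocol announced or uses the matched boluses. The main loss is masking by the worst score (about 12% to 44% of subjects with new semi-solid airway invasion in the main illustration), followed by cases where neither the worst score nor the sum rises (about 9% to 22%). Complete concealment on all three methods is uncommon (about 2% to 3%, and 1% to 7% in the second illustration). Even when the sum rises, the texture is not identified. These rates rest on assumed score distributions and independence, so they show the mechanism and not what happened in this trial. The change should be made: it is inexpensive, and the conclusion now depends on description.

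**What to change.** Add to SAP 6.5.8:

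1. A descriptive bolus-matched table giving the number of subjects worse, same or better at VFSS 2 than on the same bolus at VFSS 1, for each of boluses 1-11 and grouped as thin liquid (1-5), thin honey (6-8), and pudding and cracker (9-11).
2. A by-subject listing of the pre/post pairs, up to 99, with boluses not given because an exam ended early marked as such.
3. A rule that each bolus score is the worst of its scored swallows (1 to 7 per bolus). The existing sum of 11 needs such a rule too.
4. A note that pairs are clustered within subject and that no inference is intended.

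In SAP 6.6, name the move from the protocol's per-trial analysis to exam-level summaries, and the added table.

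The cost is one table, one listing and a few sentences, from recordings the protocol already has scored swallow by swallow. The downside is more small descriptive cells to read.

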The information in this study protocol is confidential. Any disclosure, copying or distribution of the information contained within is strictly prohibited without written consent from MonoSol Rx LLC.

[figure not shown]
Table 4 Penetration Aspiration Scale (PAS)

Airway Safety Group	PAS Score	Definition
SAFE	1	Material does not enter airway.
	2	Material enters the airway, remains above VF, and is ejected from airway.
UNSAFE	3	Material enters the airway, remains above VF and is not ejected from airway.
	4	Material enters the airway, contacts VF and is ejected from airway.
	5	Material enters the airway, contacts VF and is not ejected from airway.
	6	Material enters the airway, passes below VF and is ejected into the larynx or out of airway.
	7	Material enters the airway, passes below VF and is not ejected from airway despite effort.
	8	Material enters the airway, passes below VF and no effort is made to eject.

Safe

Penetration

Aspiration

The inclusion criteria are developed to focus the study on a cross section of ALS subjects. Exclusion criteria exclude subjects with certain medical conditions, with allergies to barium or study drug, and females who are pregnant or breastfeeding.

The primary aim of this study is to assess swallowing safety with the new ROSF formulation.

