6.6 Changes to Methods Planned in the Protocol

See previous sections regarding methods changed since the protocol.

Based upon FDA feedback Exclusion criteria #2 will be updated to the following:

Subjects with a prior swallowing study that has shown a PAS score of 4 or greater and subjects with a PAS score of 3 or greater and who have exceeded more than 2 abnormal swallows (PAS of 3 or greater) will be excluded from participation in the study.

Videofluoroscopic Swallowing Study (VFSS1 - PAS):

The 12th bolus was inadvertently included as part of the PAS evaluation. This bolus is typically included only to determine if the subject can open the mouth to the diameter of the pill. The PAS is not normally assessed during this bolus; therefore, the 12th bolus trial presentation at the end of the list will be removed from the study and the section 10.2.2. in protocol is clarified as follows:

After consent has been verified and screens completed, the patient will be seated and will complete a standardized bolus protocol that includes 11 bolus trial presentations.

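### The 4-category PAS table takes the highest score before categorising, so an exam with scores of 3 and 4 is labelled A despite a category-B swallow

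*SAP*

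**What the plan says.** SAP 6.5.8 makes the PAS analysis descriptive and presents it in three ways: single worst score, sum of the 11 scores, and a 4-category method. It describes the PAS as "an 8-point ordinal scale, where higher scores indicate lower function, measured individually for 11 swallowing trials". For the third method, the cited authors "propose categorization of single worst PAS score into 4 categories". Category A "includes scores 1, 2, 4"; B holds 3, 5 and 6; C is 7; D is 8. The table is to give the "number/percentage of patients who stay the same, increase or decrease (and by how much".

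Protocol Table 4 (section 10.3.6.2) defines PAS 3 as "Material enters the airway, remains above VF and is not ejected from airway" and PAS 4 as "Material enters the airway, contacts VF and is ejected from airway". It places both in the unsafe group.

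Protocol 13.5.1 adds that "each individual swallow within a bolus trial will be analyzed", with 1 to 7 swallows per bolus. SAP 6.5.8 counts one score per bolus.

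No rule in either document covers an exam whose highest score falls in a lower category than another of its scores.

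**The concern.** The method uses two orders that conflict. Selecting the worst score ranks 4 above 3. Reporting an increase or decrease across A to D ranks 3 above 4. When an exam contains both, the 4 is selected, it maps to A, and the category-B swallow drops out.

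Two errors follow in a safety table. In a false decrease, a subject who keeps a 3 and gains a swallow with vocal-fold contact is counted as decreased. In a hidden increase, a subject who newly shows penetration that is not ejected is counted as unchanged. The mirror-image errors arise when the pre-dose exam holds the 3 and the 4.

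Swallowing safety is the study's only objective and nothing is tested, so these tables are the result. A worst score of 3 at baseline is plausible. The exclusion updated in SAP 6.6 removes subjects with a prior PAS of 4 or more and "subjects with a PAS score of 3 or greater and who have exceeded more than 2 abnormal swallows". As I read it, a prior PAS of 3 on at most two swallows is admitted.

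Two things are not at issue. A 3 replaced by a 4 with no 3 left moves B to A by the grouping's own design. Ties within a category are inherent in the grouping and show in the single-worst-score table.

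**Working it through.** The documents state no figure for this step, so there is none to reproduce. The inputs are the grouping and the 11 scores per exam (SAP 6.5.8) and the 9 completers (SAP 6.2).

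**Which exams are affected.** There are 2^8 − 1 = 255 non-empty sets of PAS values. Applying the SAP order (highest score, then category) and the reverse order (categorise each score, then take the worst category) to every set gives different labels in exactly four: {3,4}, {1,3,4}, {2,3,4} and {1,2,3,4}. Each is A under the SAP order and B under the reverse. This counts patterns; it is not a probability.

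**Worked examples (11 scores each).**

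| | Pre | Post | Worst score | Sum | SAP order | Categorise first |
|---|---|---|---|---|---|---|
| False decrease | ten 1s, one 3 | nine 1s, one 3, one 4 | 3 to 4 | 13 to 16 | B to A | B to B |
| Hidden increase | eleven 1s | nine 1s, one 3, one 4 | 1 to 4 | 11 to 16 | A to A | A to B |

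**How often it could happen.** The documents give no bolus-level frequencies, so the rates are assumptions. Let p3 and p4 be the chances of a 3 and a 4 on a bolus, with no scores of 5–8, independent boluses, independent pre and post exams, and q = 1 − p3 − p4.

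- a = P(worst score is 3) = (q + p3)^11 − q^11
- m = P(worst is 4 and a 3 is present) = 1 − (q + p3)^11 − [(q + p4)^11 − q^11]
- c = P(no 3 in the exam) = (1 − p3)^11
- False decrease = a × m; hidden increase = c × m

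| p3, p4 | a | m | c | False decrease (of 9) | Hidden increase (of 9) |
|---|---|---|---|---|---|
| 2%, 2% | 0.162 | 0.037 | 0.801 | 0.6% (0.05) | 2.9% (0.3) |
| 5%, 5% | 0.255 | 0.176 | 0.569 | 4.5% (0.4) | 10.0% (0.9) |
| 10%, 5% | 0.401 | 0.285 | 0.314 | 11.4% (1.0) | 8.9% (0.8) |

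Counting errors in both directions, the reported status is wrong when exactly one of the two exams is mislabelled: 2m(1 − m) = 7%, 29% and 41%.

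**Adding scores of 5–8 (0.5% each, 2% in all).** Now q = 0.98 − p3 − p4.

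- Mislabelled exam = 0.98^11 − (q + p3)^11 − (q + p4)^11 + q^11 = 0.031, 0.146, 0.234
- Category B, correctly labelled = (q + p3)^11 − q^11 + 0.99^11 − 0.98^11 = 0.227, 0.300, 0.416
- Category A, correctly labelled = (q + p4)^11 = 0.638, 0.450, 0.245

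Multiplying as before (on unrounded values), false decrease is 0.7%, 4.4% and 9.7%, and hidden increase is 1.9%, 6.6% and 5.7%. Here some pre-dose B exams have a worst score of 5 or 6, so the decrease is false on the category scale even though the worst score fell.

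**Letting pre and post exams correlate.** With a shared subject effect on a probit scale (SD 1 to 1.5, an assumption), the same bolus rates and no scores of 5–8, simulation gives:

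| p3, p4 | False decrease | Hidden increase |
|---|---|---|
| 2%, 2% | about 1.1% | 1.4–2.3% |
| 5%, 5% | 2.5–3% | 2–4% |
| 10%, 5% | 4–6% | 1–2% |

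Every cell is below 0.6 subjects of 9.

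**The case against.** The strongest objection is that the numerically highest reading is inferred. The SAP is reporting a published proposal. Neither that source nor the table shells, which SAP 6.5 places in a separate document, can be consulted, and either may take the worst category. The inference is still the natural one: 6.5.8 equates higher with worse and describes categorising a single score. If worst category was meant, the sentence proposed below is still needed.

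The harm is also limited, and this stands. Three methods are shown side by side, are declared post hoc and descriptive, and the other two would show a rise in both examples. No test or stopping decision rests on this table. That lowers the stakes, but it does not excuse a table that contradicts the others without explanation.

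The upper rates are strained, and this stands too. They imply that 36%, 69% and 83% of exams contain a PAS of 3 or more (1 − q^11), and the documents do not support the higher two. Independent pre and post exams also conflict with the correlation of 0.6 assumed in Protocol 13.5.3; correlation lowers most of the rates. Excluding subjects with a prior PAS of 4 or more makes the mirror-image errors less likely, though only among subjects who had a prior study.

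Finally, the correction turns the first example into B to B, not an increase. It removes a wrong direction; it does not make this table show the added vocal-fold contact.

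**Conclusion.** The concern holds. Followed as written, the 4-category rule can report a worsening as a decrease or as no change, on the study's only objective. The mislabelling is confined to exams whose top score is exactly 4 and which also contain a 3.

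That the rule mislabels these exams depends only on reading worst as numerically highest. How often it happens is unknown. Under the assumptions shown, each error type affects between about 0.6% and 11.4% of subjects with independent exams, and at most about 6% with correlated exams. In the 9 completers that means roughly one subject or none, but a single subject is 1/9 = 11.1% of the table. It should be fixed, although no decision in the study depends on it.

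**What to change.** In the 4-category paragraph of SAP 6.5.8, state that each of the 11 bolus scores is assigned a category A to D, that the exam's category is the worst of these, and that same, increase and decrease are counted on that category. If several swallows per bolus are scored (Protocol 13.5.1), assign categories before reducing swallows to a bolus score; otherwise the same error recurs inside a bolus.

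Also list any subject for whom the three methods differ in direction. This covers what the correction alone does not show.

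The cost is one SAP sentence and a few lines of code on data already scored. The drawback is a further change made after seven results had been seen, possibly departing from the published method. It should be labelled post hoc and stated in the CSR.
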